2.1.2 Visits windows

Visit windows will be used for the data that is summarized by visit; they are based on the study evaluation schedule and comprise a set of days around the nominal visit day. For any assessment, there are the protocol defined scheduled visits around which visit windows are created in SAP to cover the complete range of days within the study. The visit windows are shown in [Table 2-1](#). These apply to measurements taken at every visit. For assessments collected less often, different visit windows will be applied as detailed below.

When visit windows are used, all visits will be re-aligned, i.e., they will be mapped into one of the visit windows. E.g., if the *Week 4* visit of a subject is delayed and occurs on Day 46 instead of on Day 29, say, it will be re-aligned to visit window *Week 8*. In the case of major deviations from the visit schedule, or due to unscheduled visits, several assessments of a subject may fall in a particular visit window (either scheduled or unscheduled). Statistical approaches to handle multiple assessments in a given visit window are specified below.

Of note, subjects are allowed to have gaps in visits.

Table 2-1 Assessment windows for scheduled visits

Analysis Visit	Week	Scheduled Day	Visit Window
Baseline	BSL	1*	
Week 1	1	8	Day 2-11
Week 2	2	15	Day 12-18
Week 3	3	22	Day 19-25
Week 4	4	29	Day 26-43
Week 8	8	57	Day 44-71**
Week 12	12	85	Day 72-113
Week 20	20	141	Day 114-151
Week 24	24	162	>=152 Days

* Baseline measurement before the first drug administration for safety assessments and before the randomization for efficacy assessments. For efficacy visit windows, refer to date of randomization.

** For primary endpoint analysis, data will be considered as Week 8 data, if Week 8 dose administration was done on or after the assessment date.

For parameters, which are not collected at every visit (e.g., FACIT-Fatigue[©], ASAS Health Index), visit windows defined in [Table 2-1](#) will be combined. For example, if a parameter is measured at Week 12 and Week 24 only, Week 12 visit window will extend from Day 2 to Day 113 (combining Week 1 to Week 12 visit windows), Week 24 will extend from Day 114 to >=152 days (combining Week 20 to Week 24). If more than one assessment falls into the interval, the rules defined in [Section 2.1.3](#) below are applied.

Table 2-2a Assessment windows for scheduled visits of Exposure Data

The administration of study drug at week 16 is not in relation to a study visit. For exposure data, a specific assessment window for week 16 is used in order to account for the home administration at week 16.

Analysis Visit	Week	Scheduled Day	Visit Window
Baseline	BSL	1*	
Week 1	1	8	Day 2-11
Week 2	2	15	Day 12-18
Week 3	3	22	Day 19-25
Week 4	4	29	Day 26-43
Week 8	8	57	Day 44-71
Week 12	12	85	Day 72-99
Week 16	16	113	Day 100-127
Week 20	20	141	>= 128 Days

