## **6 Visit schedule and assessments**

[Table 6-1](#) lists all of the assessments and indicates with an “x” when the visits are performed. During the study, the assessments must be performed as indicated in [Table 6-1](#).

Patients must be seen for all visits on the designated day, or as close to it as possible to the original planned visit.

- For visits scheduled through Week 4, the study treatment should not be administered less than 3 days after the previous administration.
- For visits scheduled after Week 4, the study treatment should not be administered less than 14 days after the previous administration.

Note: Missed or rescheduled visits should not lead to automatic discontinuation of patients.

Patients who prematurely discontinue the study for any reason should be scheduled for a visit as soon as possible, at which time all of the assessments listed for the final visit will be performed. At this final visit, all dispensed investigational product should be reconciled and the AEs and concomitant medications reconciled on the CRF. If patients refuse to return for these assessments or are unable to do so, every effort should be made to contact them or a knowledgeable informant by telephone to determine the reason. Documentation of attempts to contact the patient should be recorded in the source documentation.

No study assessment will be performed unless patients sign the ICF. Once a patient signs the ICF, he/she will be screened for eligibility criteria. The Screening Period will be flexible in terms of the time required to washout prior anti-rheumatic and other medications and will have a recommended duration of up to 10 weeks. During the Screening Visit, assessments will be performed as outlined in [Table 6-1](#). Patients who have screen-failed once may be re-screened once if, in the opinion of the investigator, the risk/benefit ratio for the patient is positive and it is likely that the patient can meet all eligibility criteria at the second screening

time point. In this case, the patient will receive a new Patient Number (new Informed Consent process, separate IRT entry and eCRF data set applies).

The duration of the washout period will be determined at the Screening Visit. Note: All patients evaluated at Screening (Visit 1) for eligibility should not be screen failed based on a medication requiring washout, unless the patient will be unable to complete the washout in the appropriate time frame before randomization.

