**Table 6-1 Assessment schedule**

	Screening	Treatment Period 1 Double-blind placebo-controlled (last dose at Week 4)					Treatment Period 2 Double-blind active (last dose at Week 20)				USV**	Comments
Visit number	1	2	3	4	5	6	7	8	9	10 EOS/ PPD*		* EOS/PPD - Patients who prematurely discontinue during the treatment period should return for assessments associated with the Week 24 visit (i.e. 4 weeks after the last study treatment). ** Unscheduled visit – assessments at the discretion of the investigator.
Week	-10 to -1	0	1	2	3	4	8	12	20	24		
Recommended visit window (days)			± 2	± 2	± 2	± 2	± 2	± 5	± 5	± 5		
Information and informed consent	X											
Inclusion & exclusion criteria	X	X										
axSpA history		X										
Spinal pain responder assessment							X					
Demographics	X											
Relevant medical history/ current medical conditions	X											
Prior medication/ concomitant medication	X	X	X	X	X	X	X	X	X	X	X	
AEs/ SAEs (including injection site reactions)	X	X	X	X	X	X	X	X	X	X	X	AEs/SAEs occurring after the patient has signed the informed consent (including those that occur during home administration of study drug) must be captured on the appropriate eCRF page. Any AEs that are treatment-emergent should be reported until 12 weeks after the last study treatment.

	Screening	Treatment Period 1 Double-blind placebo-controlled (last dose at Week 4)					Treatment Period 2 Double-blind active (last dose at Week 20)					USV**	Comments
		1	2	3	4	5	6	7	8	9	10 EOS/ PPD*		
Visit number	1	2	3	4	5	6	7	8	9	10 EOS/ PPD*			* EOS/PPD - Patients who prematurely discontinue during the treatment period should return for assessments associated with the Week 24 visit (i.e. 4 weeks after the last study treatment). ** Unscheduled visit – assessments at the discretion of the investigator.
Week	-10 to -1	0	1	2	3	4	8	12	20	24			
Recommended visit window (days)			± 2	± 5	± 5	± 5							
Smoking history		X											
Cardiovascular medical history	X												
Physical examination	S	S	S	S	S	S	S	S	S	S	S		
Height† and weight		X								X	X		† Height will be assessed at Visit 2 or unscheduled visit only.
Vital signs	X	X	X	X	X	X	X	X	X	X	X		
QuantIFERON TB-Gold test	X											X	

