2.1.3 Multiple assessments within visit windows

When there are *multiple assessments* in a particular visit window, the following rules are applied to select one value “representing” the subject in summary statistics in a visit window (see [Table 2-1](#)).

For baseline assessment definition, see [Section 2.1.1](#). For post-baseline visit windows, the following applies (unless otherwise specified):

- for *quantitative variables*, the *closest* to the actual visit is chosen (if two assessments have the same distance, then the earlier one will be chosen);
- for *qualitative variables*, the *worst* record is selected. It is noted that in the analyses performed, *worst* case is always well defined.
- in case qualitative variables are based on quantitative variables, e.g. spinal pain NRS response, the visit will be assigned to the quantitative variable, and this visit will be used for the derived qualitative variable.

Table 2-3 Rules for selecting values for analysis

Timing of measurement	Type of data	Rule
Baseline	All data	See Section 2.1 Data analysis general information
Post-baseline efficacy	All data	Cases where the same parameter is recorded more than once on the same date will be handled as follows: 
• If time of completion exists the earliest measurement will be used;• If time does not exist the measurement from the lowest CRF visit number will be used.

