2.11 Patient-reported outcomes

Variables related to health-related quality of life (HR-QoL) are described below. All HR-QoL variables will be evaluated based on the FAS-TP1 and FAS-TP2 population at (Baseline to Week 8) and (Week 8 to Week 24) respectively.

FACIT-Fatigue[®] score

- Change from baseline in FACIT-Fatigue[®] score for each treatment group at Week 8.
- Change from baseline in FACIT-Fatigue[®] score for each treatment group at Week 24.
- Change from Week 8 in FACIT-Fatigue[®] score for each treatment group at Week 24.

All FACIT scales are scored so that a high score is good.

To achieve this, we reverse response scores on negatively-phrased questions. The total score is then calculated as the sum of the un-weighted subscale scores.

Calculate the score only if at least 11 questions are answered.

Calculate the total score as mentioned in below table:

Item Number	Reverse Item?		Item Response	Item Score
1	4	-		=
2	4	-		=
3	4	-		=
4	4	-		=
5	4	-		=
6	4	-		=
7	0	+		=
8	0	+		=
9	4	-		=
10	4	-		=
11	4	-		=
12	4	-		=
13	4	-		=

Sum individual item scores: _____

Multiply by 13: _____

Divide by number of items answered: _____

Patient Accepted Symptoms State

- Proportion of patients in each treatment group with satisfactory PASS at Week 1, 2, 3, 4 and 8.
- Proportion of patients in each treatment group with satisfactory PASS at Week 12, 20 and 24.

ASAS Health Index

- Proportion of patients in each treatment group of achieving a minimal improvement (MCII) in ASAS health index at Week 8.
- Proportion of patients in each treatment group of achieving a minimal improvement (MCII) in ASAS health index at Week 24.

- Proportion of patients in each treatment group of achieving a significant improvement (SCI) in ASAS health index at Week 8.
- Proportion of patients in each treatment group of achieving a significant improvement (SCI) in ASAS health index at Week 24.
- Change from baseline in ASAS health index for each treatment group at Week 8 and Week 24.

Total Score calculation:

Total Score will be analyzed, if no more than 20% of data is missing. The total score is calculated as follows for respondents with one to a maximum of three missing responses

$$\text{Sumscore} = \{x/(N-m)\} * N$$

Where

x= Item summation score

N=Total no of items applicable (Items “I have lost interest in sex.” and “I have difficulty operating the pedals in my car” can be not applicable for few patients).

m=Number of missing Items

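### SAP Table 2-1 puts Week 24 on Day 162, which is Week 23; the correct day is 169, and the error moves the Week 20/Week 24 cut from 155/156 to 151/152.

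*SAP*

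**What the plan says.** SAP 2.1.2 states that the analysis windows follow the visit schedule: "they are based on the study evaluation schedule and comprise a set of days around the nominal visit day". Table 2-1 then lists a scheduled day and a window for each visit. Week 20 is Day 141 with window Day 114–151, and the last row reads "Week 24 24 162 >=152 Days". The exposure table that follows (Table 2-2a) adds the home dose, "Week 16 16 113 Day 100-127".

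All visits are re-labelled by study day. The SAP's own illustration is a Week 4 visit moved to Week 8: "visit of a subject is delayed and occurs on Day 46 instead of on Day 29". When several records fall in one window, SAP 2.1.3 takes the record nearest to the actual visit for quantitative variables, with ties going to the earlier record; "for *qualitative variables*, the *worst* record is selected".

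Protocol Table 6-1 places the last dose at Week 20 and the final visit at Week 24, four weeks after the last treatment. Both visits have a recommended window of ±5 days. SAP section 4 declares no change to the protocol-specified analyses.

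**The concern.** The scheduled day for Week 24 does not fit the rest of its own table or the protocol schedule, and no text explains Day 162 or places a visit at Week 23. The window limit appears to have been built from the wrong day, so the mistake is in the rule that assigns records to visits and not only in a label.

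This matters for late visits, which both documents foresee. The SAP example is 17 days late (46 − 29), and Protocol section 6 says "Missed or rescheduled visits should not lead to automatic discontinuation of patients". A sufficiently late Week 20 record would leave the Week 20 summary and enter the Week 24 summary. PASS is the most exposed, because it is reported at both visits ("Proportion of patients in each treatment group with satisfactory PASS at Week 12, 20 and 24") and the worst record in a window is the one used. An unsatisfactory answer from a late Week 20 visit would then override a satisfactory answer given on time at Week 24.

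**Working it through.** **Inputs.** Scheduled days and windows from SAP Tables 2-1 and 2-2a; the day convention in SAP 2.1.1 (first dose is Day 1, no Day 0); visit windows of ±5 days at Weeks 20 and 24 from Protocol Table 6-1. For efficacy, Table 2-1 counts from randomization, which does not alter the spacing between visits.

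**Step 1: scheduled days.** With Day 1 as origin, Week w falls on Day 7w + 1.

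| Week | 7w + 1 | Day in SAP |
|---|---|---|
| 1 | 8 | 8 |
| 2 | 15 | 15 |
| 3 | 22 | 22 |
| 4 | 29 | 29 |
| 8 | 57 | 57 |
| 12 | 85 | 85 |
| 16 (Table 2-2a) | 113 | 113 |
| 20 | 141 | 141 |
| 24 | **169** | **162** |

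Only Week 24 fails. (162 − 1)/7 = 23.0, so Day 162 is exactly Week 23. Counting from the last dose gives the same answer as the formula: 141 + 28 = 169. The protocol's Week 24 range is 169 ± 5 = Days 164–174, and Day 162 lies outside it. Counting 7 × 24 without the extra day gives 168, and taking the early edge of the protocol window gives 164; neither produces 162.

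**Step 2: the cuts.** Midpoint of neighbouring scheduled days, against the last day of the earlier window in Table 2-1:

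| Neighbouring days | Midpoint | Window ends |
|---|---|---|
| 8, 15 | 11.5 | 11 |
| 15, 22 | 18.5 | 18 |
| 22, 29 | 25.5 | 25 |
| 29, 57 | 43 | 43 |
| 57, 85 | 71 | 71 |
| 85, 141 | 113 | 113 |
| 141, 162 | 151.5 | 151 |

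All seven are the midpoint rounded down, and an exact midpoint goes to the earlier visit. The later cuts in Table 2-2a (99 and 127) follow the same pattern. The SAP's 151/152 cut is therefore reproduced, but only from Day 162. With Day 169 it is (141 + 169)/2 = 155, giving Week 20 = Day 114–155 and Week 24 = Day 156 onward.

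**Step 3: which records move.** Days 152–155. Days 152, 153 and 154 are 11, 12 and 13 days from Day 141 and 17, 16 and 15 days from Day 169, so they are nearer Week 20. Day 155 is 14 days from both and goes to Week 20 by the tie pattern in step 2. A Week 20 visit must be 152 − 141 = 11 to 155 − 141 = 14 days late to land there. If that patient has no later record, a value taken 14–17 days before Day 169 stands as the Week 24 value.

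**Step 4: visits within the protocol windows.** Week 20 on Days 136–146 lies inside 114–151, and Week 24 on Days 164–174 lies inside the window from 152. Neither is mislabelled.

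**Step 5: choice among several records, conditional.** If nearness in SAP 2.1.3 is measured to the tabled day, an on-time Day 169 value is 7 days from Day 162. It then loses to any other record with |d − 162| ≤ 7 before Day 169, that is Days 155–168 (Day 155 by the tie rule). With the target at 169 no such record wins. If nearness is measured to the visit actually held, this displacement does not arise.

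**The case against.** The arithmetic is hard to contest; the case on the other side is about size.

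- **The midpoint rule is inferred.** The SAP does not state it, nor the tie rule that sends Day 155 to Week 20. That is correct, but the pattern fits every cut in both tables, and Days 152–154 are nearer Week 20 without any tie rule.
- **Moving late visits to the next window is deliberate.** After correction, a Week 20 visit on Day 156 would still count as Week 24, 13 days before Day 169, so the correction only trims the extreme from 17 days to 13. Elsewhere the table accepts Day 113 as Week 12 (28 days after Day 85) and Day 114 as Week 20 (27 days before Day 141). This stands, and it keeps the point small.
- **Early-discontinuation visits.** These carry the Week 24 assessments. One held on Days 152–155 now receives its nominal label and would become Week 20 after correction. That is the result of labelling by study day, which the SAP has chosen; it does not support Day 162.
- **The PASS example is uncommon.** It needs a Week 20 visit 11–14 days late, a Week 24 visit still on time, and an answer that turns from unsatisfactory to satisfactory. The documents give no basis for a frequency. This also stands.

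None of this makes Day 162 a correct entry for Week 24.

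**Conclusion.** The point holds, at minor severity. Day 162 is Week 23, Week 24 is Day 169, and the 151/152 cut carries the error into the assignment rule. Four study days (152–155) are labelled Week 24 when the table's own construction assigns them to Week 20; for Day 155 this rests on the tie pattern seen in the other cuts.

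The measures exposed to the cut are those collected at both visits: spinal pain NRS, BASDAI, PASS and vital signs. FACIT-Fatigue and the ASAS Health Index are collected after baseline only at Weeks 8 and 24 and use combined windows, so the cut does not reach them. The effect through the choice among several records (step 5) depends on how SAP 2.1.3 is read and is not needed for the conclusion. How many patients are affected depends on how many visits are 11–14 days late, which cannot be known from the documents.

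**What to change.** In SAP Table 2-1, change three entries: Week 24 scheduled day to 169, Week 20 window to Day 114–155, and Week 24 window to Day 156 onward. For consistency, change 152 to 156 in the combined-window example in SAP 2.1.2; this alters no result, because that combined window starts on Day 114.

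While the table is open, one optional drafting change: the footnote that limits Week 8 data to assessments on or before the Week 8 dose names only the primary endpoint. The Treatment Period 1 definition in SAP 2.1.1, and the statement in SAP 2.7 that BASDAI is analysed like the primary endpoint, already imply the same limit for BASDAI. Saying so for all Week 8 efficacy endpoints removes doubt.

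The cost is a few numbers and one phrase, with no new data and no change to the confirmatory tests.

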### **9.4.3 Handling of missing values/censoring/discontinuations**

For the primary endpoint, patients with missing assessments at Week 8 will be considered as non-responders.

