2.1.1 General definitions

Study treatment: Study treatment refers to:

Secukinumab 150 mg provided in 1 ml PFS or secukinumab placebo provided in 1 ml PFS.

Study treatment start and end date: Study treatment start date is defined as the first date, when a non-zero dose of study drug is administered and recorded on the Drug Administration Record (DAR) CRF page. Similarly, study drug end date is defined as the last date, when a non-zero dose of study drug is administered and recorded on the DAR CRF page of the core study.

Study day: Study day will be calculated as (event date – study drug start date + 1 day) for events that occurred on or after study drug start date (e.g., visit, lab samples, AEs). For events prior to study drug start date (e.g., time of diagnosis), study day will be negative and calculated as (event date – study drug start date). Note that study drug start date is study day 1 and the day before study drug start date is study day -1 (i.e. no study day 0).

Due to the study drug dosing schedule, one month will be considered as 28 days. However, for “time since event” data (e.g., medical history), one month will be considered as 365.25/12 days for events that occurred prior to study Day 1. Time from events prior to the start of study drug, e.g., time since diagnosis, is calculated as the difference between the start date of study drug and the date of prior event.

Note that, the first dose day is Day 1, and the day before the first dose day is counted as Day - 1 (not Day 0).

Baseline and post baseline: In general, a *baseline* value refers to the last measurement made prior to administration of the first dose of study treatment. A post-baseline value refers to a measurement taken after the first dose of study treatment.

Treatment Period: There are 2 treatment periods for this study defined as:

Treatment Period 1 is defined as an 8-week placebo-controlled, double-blind treatment period starting from baseline till Week 8. Assessments of Week 8 are included in TP1 whereas administration of study drug at week 8 will be a part of TP2. Week 8 is the last visit of TP1 for all assessments except drug intake.

Treatment Period 2 is a 16 week double-blinded, active treatment period starting from Week 8 till Week 24 for administration of study drug. Week 8 assessments are considered as the baseline values for assessments during TP2.

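### The pre-dose condition for Week 8 data covers only the primary endpoint and has no branch for patients who receive no Week 8 dose

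*SAP*

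**What the plan says.** - **Window.** SAP Table 2-1 sets Week 8 at Day 57 with a window of Day 44 to Day 71. Unscheduled records are mapped into the windows along with scheduled ones. For parameters collected less often, the windows are merged. On the pattern of the SAP's own example, a parameter collected at Week 8 and Week 24 only (FACIT-Fatigue, ASAS Health Index) has a Week 8 window of Day 2 to Day 71.
- **Pre-dose condition.** The footnote reads: "For primary endpoint analysis, data will be considered as Week 8 data, if Week 8 dose administration was done on or after" the assessment date.
- **Choice among several records.** SAP 2.1.3: "for *quantitative variables*, the *closest* to the actual visit is chosen". For qualitative variables such as PASS, the worst record is taken. Neither rule refers to dosing.
- **Period definition.** SAP 2.1.1: "Week 8 is the last visit of TP1 for all assessments except drug intake". The same section makes Week 8 assessments the baseline for Treatment Period 2.
- **Unscheduled visits.** Protocol Table 6-1 provides for spinal pain, BASDAI, PASS, patient global, hsCRP, FACIT-Fatigue and ASAS Health Index at unscheduled visits, with "assessments at the discretion of the investigator".
- **Missing data.** Protocol 9.4.3: "patients with missing assessments at Week 8 will be considered as non-responders". SAP 2.5.3 likewise treats a patient with no Week 8 value as a non-responder, and SAP Section 4 declares no change from the protocol.

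**The concern.** The placebo comparison is valid only up to the Week 8 dose, when every placebo patient still on treatment moves to secukinumab. The footnote shows that this risk was recognised for the primary endpoint. The same protection is not written for the hierarchically tested BASDAI endpoint, for the repeated-measures analysis that serves as the primary endpoint's sensitivity analysis, or for the other Week 8 outcomes. A post-dose value could enter any of these, and could also become the Treatment Period 2 baseline.

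The second problem lies in the primary endpoint itself. The footnote makes eligibility depend on a dose having been given. A patient with an observed Week 8 score but no Week 8 dose does not meet the condition, so the score is set aside and non-response is imputed. That is a rule about stopping treatment, created by a window footnote and not stated as a choice.

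**Working it through.** **1. Which post-dose records can fall in the window.** Visit 7 is allowed at Day 57 ± 2. A dose on Day 55, 57 or 59 leaves 71 − 55 = 16, 71 − 57 = 14 or 71 − 59 = 12 post-dose days inside the window. The next scheduled assessment is Week 12 at Day 85 ± 5 (Day 80 to 90), outside it. With visits on schedule, only unscheduled visits can supply post-dose records.

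**2. How such a record becomes the Week 8 value.**
- The Visit 7 value is missing and an unscheduled post-dose record lies in the window.
- The distance in SAP 2.1.3 is measured from nominal Day 57. With Visit 7 and dosing on Day 55 (distance 2) and an unscheduled visit on Day 58 (distance 1), Day 58 is chosen. If distance is measured from the day Visit 7 took place, Day 55 has distance 0 and is kept. The wording allows both readings.
- For PASS, a later answer is worse than the Visit 7 answer. This route cannot bring in drug benefit, because a better answer never replaces a worse one.

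**3. The plan's own sample size.** Inputs (Protocol 9.8, SAP Section 3): p0 = 0.235, p1 = 0.436, difference d = 0.201, 3:1 allocation, two-sided 5%, 90% power. The pooled rate is (0.235 + 3 × 0.436)/4 = 0.38575.

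n0 = [1.960 √((4/3) × 0.38575 × 0.61425) + 1.282 √(0.235 × 0.765 + 0.436 × 0.564/3)]² / 0.201² = 76.4.

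Continuity correction: (76.4/4) × [1 + √(1 + 8/(3 × 76.4 × 0.201))]² = 82.9, rounded up to 83. The total is 83 + 249 = 332, as stated. At 88 and 264 patients the same formula without the correction gives 93.7% power, with an odds ratio of 2.52.

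**4. Size of post-switch substitution.** The documents give neither the share affected nor BASDAI planning rates, so the shares below are assumed and the spinal pain rates are used. As an upper bound, affected placebo patients respond at the active rate: p0′ = 0.235(1 − c) + 0.436c.

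| Share c of placebo arm | p0′ | Odds ratio | Power |
|---|---|---|---|
| 0 | 23.5% | 2.52 | 93.7% |
| 1% | 23.7% | 2.49 | 93.2% |
| 5% | 24.5% | 2.38 | 90.9% |
| 10% | 25.5% | 2.26 | 87.2% |

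**5. Whether undosed patients with a score can occur.** Protocol 5.5.6 and 7.6 let patients stay in the trial off study drug. Protocol 5.6.2 places the discontinuation visit 4 weeks after the last dose: a last dose on Day 22 or Day 29 gives Day 50 or Day 57, both inside Day 44 to 71 with no Week 8 dose. (Protocol Section 6 asks for that visit as soon as possible; the two timings must be reconciled.)

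**6. Size of the undosed case.** A share u with an observed score is forced to non-response, so p′ = p(1 − u). The 5.7% is the recruitment allowance, 20/352, used only as a reference point.

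| Share u | Placebo / active rate | Odds ratio | Power |
|---|---|---|---|
| 2%, both arms | 23.0% / 42.7% | 2.49 | 93.0% |
| 5.7%, both arms | 22.2% / 41.1% | 2.45 | 91.5% |
| 5.7%, active only | 23.5% / 41.1% | 2.27 | 86.5% |
| 5.7%, placebo only | 22.2% / 43.6% | 2.72 | 96.5% |

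In patients: 1% to 3% of 352 is 3.5 to 10.6. At the pooled rate of 0.386, that is about 1 to 4 observed responders recoded.

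**The case against.** The strongest defence is that the rest of the plan already implies the restriction. SAP 1.1 ends Treatment Period 1 at the Week 8 drug administration, SAP 2.1 focuses comparative efficacy on that period, and SAP 2.7 analyses BASDAI in the same way as the primary endpoint. Protocol 5.5.4 requires assessments before injection at every visit, and the Week 8 dose is given at the centre. On this view the gap is a missing cross-reference.

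Part of this stands. The order of procedures protects the Visit 7 value itself, and the schedule makes later records in the window uncommon. But the period definitions do not say what happens to a post-dose record that the window rules map to Week 8. SAP 2.7.2 explains the analogy with the primary analysis as the logistic model and gives no data rule. The other Week 8 endpoints lack even that link.

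On the undosed patient, the defence is that the footnote's evident purpose is to exclude post-dose values, and the SAP nowhere says that such a patient's score is discarded. That is fair as to intent. The literal condition still fails, and a programmer has no other text to follow.

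A reader might infer that half the window (14 of 28 days) is contaminated, or that a false superiority claim becomes easier. The documents support neither. The days after the switch hold no scheduled assessment, and drug benefit entering the placebo arm narrows the difference.

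**Conclusion.** The gap is real and should be closed, but its likely effect is small. As written, the rules permit a post-dose Week 8 value for every Week 8 efficacy endpoint except the primary one, including the confirmatory BASDAI endpoint. They do not make it routine: it needs a missing Visit 7 value, the nominal-day reading of distance, or a worse later PASS answer.

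Within the assumed range of 1% to 5% of placebo patients, the upper-bound loss is from 93.7% power to between 93.2% and 90.9%. The direction is towards no difference. Group A records after Week 8 also follow a further dose, at 300 mg for some non-responders, so the net effect could be smaller still.

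The undosed case concerns the primary endpoint and rests on the literal wording. Its direction is not fixed: it depends on which arm has more such patients, and the documents give no basis for expecting an imbalance. It would be too strong to say that the plan intends to discard these scores. What can be said is that the footnote, followed as written, conflicts with the protocol's restriction of imputation to missing assessments.

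**What to change.** Replace the footnote with a rule of this kind:

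*For all Treatment Period 1 analyses, an assessment dated after the first Treatment Period 2 dose is not eligible for the Week 8 window, including combined windows. The closest or worst rule is applied to eligible records only. If no Treatment Period 2 dose was given, an assessment in the applicable Week 8 window is eligible.*

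Three further statements are needed:
- Name the single day from which distance is measured, nominal or actual visit.
- State whether scores observed after use of a prohibited biologic count as observed or as non-response. This is a decision about an intercurrent event that a date filter cannot settle, and it must be made before unblinding.
- State where excluded records go. The Week 12 window in Table 2-1 starts at Day 72, so records excluded up to Day 71 would otherwise belong to no window.

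The cost is a few SAP sentences and a filter on dose dates that are already collected (Protocol 6.3). The downside is small: a few Week 8 values become missing, which means non-response for the binary endpoints analysed that way.
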